1.3. Schedule of Activities (SoA)

Period	Screening (-28 to -2 days)	Double-blinded – Placebo-controlled Period ^x																Safety Follow-up ^x			ET ^o	
		0	1	2	3	4	5	6	7	8	9	10	11	12	13	14	15	16	17 ^y	18 ^y	19 ^y	
Week																						-
Visit Windows (days) ^x		±3	±3	±3	±3	±3	±3	±3	±3	±3	±3	±3	±3	±3	±3	±3	±3	±3	±3	±3		
Study Procedure																						
Screening/ Administrative																						
ICF ^a	X																					
ICF for optional pharmacogenomic research ^c	X																					
ICF for optional total body photography substudy ^c	X																					
ICF for skin barrier function substudy ^c	X																					
FSH (post menopausal females only)	X																					
Review medical history requirements	X	X																				
Inclusion/ exclusion criteria ^b	X	X																				
Study Treatment Administration																						
Randomization		X																				
Dispense/administer study intervention ^{d,t}		X ^s	X ^s	X	X	X	X	X	X	X	X	X	X	X	X	X	X	X	X	X		
Efficacy Evaluations																						
EASI	X	X		X		X		X		X		X		X		X		X		X	X	
vIGA AD	X	X		X		X		X		X		X		X		X		X		X	X	
SCORAD	X	X		X		X		X		X		X		X		X		X		X	X	
Hand dermatitis IGA		X			X			X			X			X		X		X		X	X	
Total body photography (if available/applicable) ^c		X								X							X				X	
DLQI ^f			X							X				X		X		X		X	X	
POEM ^f		X								X			X		X		X		X		X	
PGIS ^f		X								X			X		X		X		X		X	
PROMIS 29 ^f		X								X			X		X		X		X		X	

Eczema Skin Pain and Itch NRS ^g	X	X																	
ADIS ^g	X	X															X	X	
Period	Screening (-28 to -2 days)	Double-blinded Placebo-controlled Period ^x															Safety Follow-up ^x		
Week		0	1	2	3	4	5	6	7	8	9	10	11	12	13	14	15	16	ET ^o
Visit Windows (days) ^y		±3	±3	±3	±3	±3	±3	±3	±3	±3	±3	±3	±3	±3	±3	±3	±3	±3	EOS
Study Procedure																			
Safety Evaluations																			
Physical examination	X	X																X	X
Height	X																		
Weight	X	X																X	X
Vital signs ^v (except Weeks 0 and 1)	X	X ^s	X ^s	X	X	X	X	X	X	X	X	X	X	X	X	X		X	X
TB evaluation	X	X	X	X	X	X	X	X	X	X	X	X	X	X	X	X	X	X	X
Chest radiograph	X																		
12 lead ECG (triplicate)	X	X ^u																	
Serum pregnancy test	X																		
Urine pregnancy test ^e		X	X	X	X	X	X	X	X	X	X	X	X	X	X	X		X	X
Clinical Laboratory Tests																			
QuantiFERON TB [®] test ⁱ	X																		
Hepatitis B and C serology	X																		
HIV antibody test	X																		

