Hematology	X	X	X	X	X	X		X	X	X	X	X	X	X	X			X	X
Chemistry	X	X	X	X	X	X		X	X	X	X	X	X	X	X			X	X
Fasting Lipid panel ^z	X		X					X								X			
Pharmacokinetics/ Immunogenicity																			
Serum bermekimab concentration ^j		X	X			X			X			X			X			X	X
Population PK sample ^{j,k}									X										
Antibodies to bermekimab ^j		X			X			X			X		X		X			X	X
Pharmacodynamics and Biomarkers (eg, plasma, serum, urine, biopsy sample collection)																			
Serum Biomarkers ^l		X	X			X			X						X				X
Blood sample for RNA ^l	X				X										X				
Whole blood (PBMC) ^l	X				X										X				
Pharmacogenomics																			
Whole blood (pharmacogenomics) ^m		X																	
Biomarkers																			
Tape stripping ^{nr}		X			X										X				

Skin biopsy schedule 1 ^{n,p}		X						X													
Skin biopsy schedule 2 ^{n,q}		X																	X		
Skin barrier assessment ^{h,r}		X ^w	X	X	X	X ^w	X	X	X	X	X	X	X	X	X	X	X	X ^w			
Ongoing Participant Review																					
Concomitant therapy	X	X	X	X	X	X	X	X	X	X	X	X	X	X	X	X	X	X	X	X	
AEs	X	X	X	X	X	X	X	X	X	X	X	X	X	X	X	X	X	X	X	X	

Footnotes:

- a. Must be signed before first study related activity.
- b. Minimum criteria for the availability of documentation supporting the eligibility criteria are described in Source Documentation in Section 10.3, Appendix 3: Regulatory, Ethical, and Study Oversight Considerations (Study Governance Considerations). Check clinical status again before first dose of study medication.
- c. Must be signed before first study related activity. Separate informed consents are required for participants who chose to participate in the optional pharmacogenomic research, optional skin barrier function assessments, and optional total body photography substudies.
- d. Study intervention administrations must occur no less than 4 days apart.
- e. Women of childbearing potential must have a negative urine pregnancy test result before randomization and before receiving study intervention at all study intervention administration visits. This assessment can be performed any other time during the study visit including prior to PRO collection.
- f. All PROs should be collected during the study visit prior to all other assessments, unless otherwise specified.
- g. These assessments should be completed once and twice daily for NRS and ADIS, respectively, beginning at the screening visit.

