4. STUDY DESIGN

4.1. Overall Design

This is a Phase 2, double-blind, randomized, placebo-controlled, multicenter, interventional study designed to assess the efficacy, safety, PK, biomarkers, and immunogenicity of multiple doses of bermekimab administered via IV infusion for the treatment of moderate-to-severe AD in adult participants. The participant population will be comprised of men and women ≥ 18 years of age, with moderate-to-severe AD, that has been present for at least 1 year before the first administration of study intervention, as determined by the investigator through participant interview and/or review of the medical history. Participants must also have a history of inadequate response to treatment for AD with topical medications or for whom topical treatments are otherwise medically inadvisable, an EASI score ≥ 16 , an IGA score ≥ 3 , and an involved percent body surface area (BSA) $\geq 10\%$ at both screening and at baseline. Participants must agree to apply moisturizers at least once daily for at least 7 days before randomization and continue the treatment throughout the study.

A target of approximately 60 participants will be randomly assigned in this study. The study has 3 periods namely: a screening period of up to 4 weeks, a double-blinded placebo-controlled period of 16 weeks, and a Safety Follow-Up period of 4 weeks, which includes an End of Study (EOS) visit. The study will have 3 parts within the double-blinded placebo-controlled period that will run in parallel and/or staggered: A, B, and C.

All participants will receive a weekly IV infusion of either bermekimab or placebo, in a 4:1 randomization ratio. Part A will consist of approximately 10 participants receiving bermekimab 800 mg IV weekly or placebo. Part B will consist of approximately 30 participants receiving bermekimab 1200 mg IV weekly or placebo. An analysis of the data from all 10 participants of Part A and the first 10 participants of Part B will support optimization and selection of the bermekimab dose for Part C. Selection of the Part C bermekimab dose will be based on PK, PD, efficacy, and safety analysis. Part C will consist of approximately 20 participants receiving bermekimab or placebo at a higher or lower dose (not < 800 mg) than Part B, but with a maximum dose of 2400 mg IV weekly.

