5. STUDY POPULATION

Screening for eligible participants will be performed within 4 weeks before administration of the study intervention. Refer to Section 5.4, Screen Failures for conditions under which the repeat of any screening procedures is allowed.

The inclusion and exclusion criteria for enrolling participants in this study are described below. If there is a question about these criteria, the investigator must consult with the appropriate sponsor representative and resolve any issues before enrolling a participant in the study. Waivers are not allowed.

For a discussion of the statistical considerations of participant selection, refer to Section 9.1, Sample Size Determination.

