6.8.2. Required Treatment

All participants are required to apply moisturizers at least once daily for at least 7 days before randomization and continue the treatment throughout the study (including the safety follow-up period). All types of non-prescription moisturizers are permitted, excluding any moisturizer that contains a corticosteroid.

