5.4.1.3. Eczema Skin Pain and Itch Numeric Rating Scale

The Eczema Skin Pain and Itch NRS is a two-item patient-reported outcome developed by the sponsor that participants will use to rate the severity of their eczema-related skin pain and eczema-related itch daily. Participants will be asked the following questions:

- Please rate the severity of your eczema-related **skin pain** at its worst in the past 24 hours.
- Please rate the severity of your eczema-related **itch** at its worst in the past 24 hours.

Each item is on a 0 to 10 NRS ranging from 0 “none” to 10 “worst possible” and will be scored separately. Participants will complete the rating scale daily from the screening visit through the last study visit as detailed in the protocol SoA.

The baseline is defined as the average score of last 7 days prior to Week 0 study agent administration. If there are more than 3 days missing data, then baseline is set as missing. Missing baseline will not be imputed.

Seven daily NRS scores are averaged into a weekly score (ie 7 days [from day -7 to -1] prior to a visit). Four days out of 7 days (either consecutive or nonconsecutive) are necessary to derive a weekly score; otherwise data are considered missing for that week.

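### A screening visit as late as Day -2 leaves too few diary days for the itch and pain NRS baseline, and the window is not reconciled with the 7-day moisturizer requirement

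*Protocol*

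**What the plan says.** **Screening window.** The schedule of activities (Protocol 1.3) gives "Screening (-28 to -2 days". The other sections set only an upper limit: Protocol 4.1 describes "a screening period of up to 4 weeks", and Protocol Section 5 states "Screening for eligible participants will be performed within 4 weeks before administration of the study intervention". I found no minimum length.

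**Diary start.** Footnote g of the schedule covers the daily itch and pain NRS and the ADIS: "These assessments should be completed once and twice daily for NRS and ADIS, respectively, beginning at the screening visit". Protocol Section 8 has the electronic device handed out during screening, so no earlier entries can exist.

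**Baseline rule.** SAP 5.4.1.3 takes the NRS baseline as the mean daily score over the week leading up to the first dose, and adds: "If there are more than 3 days missing data, then baseline is set as missing. Missing baseline will not be imputed".

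**Moisturizer.** Protocol 6.8.2 states: "All participants are required to apply moisturizers at least once daily for at least 7 days before randomization". Protocol 4.1 words it as an undertaking: "Participants must agree to apply moisturizers at least once daily for at least 7 days before randomization". Protocol 5.3, item 6, repeats the requirement in a list of restrictions that apply while the participant is on study.

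**Planned output.** After early termination, the SAP (Section 1, 5.3.2, 5.4.2 and Appendix 2) provides listings and no formal analyses.

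**The concern.** The latest permitted screening day and the baseline rule do not fit together. The schedule accepts a participant whose NRS baseline the SAP must then set to missing, whatever the participant does.

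The endpoints at stake are:

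- the secondary itch responder endpoint (a reduction of at least 4 points among participants with baseline itch of at least 4);
- the exploratory itch NRS change at Week 8;
- the exploratory pain NRS changes at Weeks 8 and 16.

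The comparator is small. With 12 pooled placebo participants planned (Protocol 9.2), each one lost removes 1/12 = 8.3% of that group from these endpoints.

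The same window also leaves the moisturizer requirement open to two readings, one of which the Day -2 limit contradicts.

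**Working it through.** **Inputs.** Window Day -28 to Day -2 and diary start at screening (Protocol 1.3); the 7-day baseline and its missing-data rule (SAP 5.4.1.3); no Day 0, with Day -1 the day before the first dose (SAP 5.1.3).

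**Step 1: entries required.** Baseline is missing when more than 3 of 7 days are missing, so 7 - 3 = 4 entries are needed. This agrees with the SAP's own 4-of-7 rule for weekly scores.

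**Step 2: permitted screening days.** 28 - 2 + 1 = 27.

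**Step 3: entries available.** For a screen on Day -k, with a baseline window of Days -7 to -1, the maximum is n = min(k, 7). This counts an entry made on the screening day itself, which favours the plan.

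**Step 4: chance of a valid baseline.** P(X ≥ 4) is the sum over j = 4 to n of C(n, j) p^j (1 - p)^(n - j). The documents give no daily completion rate, so p = 0.7, 0.8 and 0.9 are assumptions. For example, with n = 4 and p = 0.8, P = 0.8^4 = 0.410.

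| Screened on | Entries possible (n) | Days missing | Baseline possible? | P at p = 0.7 / 0.8 / 0.9 |
|---|---|---|---|---|
| Day -2 | 2 | 5 | No | 0 / 0 / 0 |
| Day -3 | 3 | 4 | No | 0 / 0 / 0 |
| Day -4 | 4 | 3 | Only with no missed entry | 0.240 / 0.410 / 0.656 |
| Day -5 | 5 | 2 | Yes | 0.528 / 0.737 / 0.919 |
| Day -6 | 6 | 1 | Yes | 0.744 / 0.901 / 0.984 |
| Day -7 or earlier | 7 | 0 | Yes | 0.874 / 0.967 / 0.997 |

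**Step 5: sensitivity to the Week 0 entry.** The SAP's explicit Day -7 to -1 wording belongs to the weekly score, not to the baseline sentence, and the schedule marks the NRS at Week 0. If a pre-dose Week 0 entry counts, n = min(k + 1, 7).

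- Day -2 gives 3 entries and still fails.
- Day -3 gives 4 entries (0.240 / 0.410 / 0.656).
- Day -4 gives 5 entries (0.528 / 0.737 / 0.919).

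A baseline is therefore impossible on 1 or 2 of the 27 permitted days, depending on the convention.

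**Step 6: moisturizer days.** A screen on Day -2 to Day -6 leaves 2 to 6 days on study before randomisation at Week 0. That is 5 of the 27 permitted days with fewer than 7.

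- If the requirement runs forward from the participant's agreement, the schedule contradicts it on those 5 days.
- If earlier use counts, it can be met on any permitted day.

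The documents do not choose between these readings.

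**The case against.** The strongest reply is that the moisturizer rule may itself act as a minimum screening length. It is mandatory, it is tied to eligibility through the lifestyle restrictions, eligibility is rechecked at Week 0, and waivers are not allowed. If the 7 days must follow agreement, nobody compliant is randomised early enough to lose the diary days. This is a fair point, and it means that the diary and moisturizer problems do not both bite under the same reading. But then the Day -2 limit is itself wrong; if earlier use counts, the diary gap remains. Either way the passages need reconciling.

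Practicality is the second reply. Central laboratory results, tuberculosis and viral tests, a chest radiograph and, for some, a 4-week topical washout make a 2- or 3-day screen unlikely. This stands: the documents give no distribution of screening length, so no expected number of losses can be stated.

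A reader might also infer more than the documents support:

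- **That every short screen loses its baseline.** Screens of 4 to 6 days can still yield one.
- **That there is no run-in on study.** Some days on study always remain, and no section excludes use before screening.
- **That the treatment comparison is biased by moisturizer.** Both randomised arms must use it throughout, so any late improvement would be shared.
- **That the ADIS baseline fails too.** The SAP gives no ADIS baseline rule.
- **That entry severity is poorly confirmed.** No document sets a minimum spacing between the screening and baseline readings.

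**Conclusion.** The inconsistency is real and narrow. A participant screened on Day -2 cannot have an itch or pain NRS baseline. One screened on Day -3 cannot either, unless a pre-dose Week 0 entry counts. One screened on Day -4 can have one only with few or no missed entries.

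This rests on day counting alone; only the probabilities depend on the assumed completion rates. The moisturizer conflict is conditional on the forward-running reading.

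The consequence for this trial is small. The primary endpoint is unaffected, the 4-of-7 rule appears only in the SAP, and that SAP lists data without formal analysis. A reader might infer that participants drop out of a planned comparison, but no such comparison remains. A missing baseline would still leave itch responder status undetermined in the listing. The point matters mainly for the protocol as designed and for any reuse of this schedule.

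**What to change.** Change the screening cell in the schedule of activities so that the latest screening day is Day -7, for example -28 to -7 days. All 7 baseline diary days then become available. If the screening-day entry were not counted, 6 would remain, still above the 4 required.

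Reconcile the window with the moisturizer passages in Protocol 4.1, 5.3 and 6.8.2, so that they say whether use before screening counts. In SAP 5.4.1.3, state whether a pre-dose Week 0 entry belongs to the baseline.

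The cost is one schedule cell and clarifying text, with no new visit or procedure. The fastest screeners wait up to 7 - 2 = 5 more days. I would not add a diary-count eligibility check at Week 0: it could exclude otherwise eligible participants, and the window change alone removes the structural gap.

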The study also includes 4 mandatory skin biopsies (2 at baseline and 2 post-dosing). All participants of Part A and the first 10 participants of Part B will have skin biopsies done at Week 0 (1 lesional and 1 non-lesional), and at Week 6 (2 lesional). The rest of the participants will be biopsied at Week 0 (1 lesional and 1 non-lesional), and at Week 16 (2 lesional).

All participants will have an extended in-clinic observation period of approximately 4 hours during the first 2 infusions. In this period, vital signs will be taken at the following time points: 0 hour (start of infusion), 30 minutes (mins), 1 hour, 1 hour and 30 mins, 2 hours (end of infusion), 2 hours and 30 mins, 3 hours, 3 hours and 30 mins, and 4 hours (post-infusion). Beyond the first 2 infusions, all participants will have approximately a 1 hour infusion period and at least a 1 hour observation post infusion, as well as vital signs taken approximately every 30 minutes.

An internal and Independent Data Review Committee (DRC) will be commissioned for this study.

NUMBER OF PARTICIPANTS

A target of approximately 60 participants will be randomly assigned in this study.

INTERVENTION GROUPS AND DURATION

Approximately, 10 participants are planned to receive weekly 800 mg of IV bermekimab or placebo in Part A. Approximately, 30 participants are planned to receive weekly dose of 1200 mg of IV bermekimab or

placebo in Part B. After the initial 10 participants (8A [active]:2P [placebo]) have completed 6 weeks of dosing in Part B, safety, PK, PD and efficacy will be analyzed to determine an appropriate dose to be used in Part C. Approximately, 20 participants are planned to receive the determined dose of bermekimab or placebo in Part C. The maximum dose to be considered for Part C will be 2400 mg IV weekly.

EFFICACY EVALUATIONS

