- n. Biopsy and tape strip samples to be collected pre dose. At Week 0, lesional and non lesional skin samples will be collected. At later timepoints, lesional skin samples will be collected.
- o. Participants who discontinue study intervention but do not terminate study participation are strongly encouraged to return for all protocol specified procedures for the safety follow up period and also for the ET Visit 5 weeks after last dose was administered. The procedures and evaluations listed for the ET visit should also be performed approximately 5 weeks after the last dose of study intervention. Participants who terminate study participation early should complete the procedures and evaluations listed for the ET visit approximately 5 weeks after their last administration of study intervention.
- p. Skin biopsy for all 10 participants of Part A and first 10 participants of Part B. At Week 0, lesional and non lesional skin samples will be collected. At Week 6, lesional skin samples will be collected.
- q. Skin biopsy for no participants in Part A, 20 last participants in Part B, and all participants in Part C. At Week 0, lesional and non lesional skin samples will be collected. At Week 16, lesional skin samples will be collected.

- r. Skin barrier function assessment should be evaluated together with tape stripping. Skin barrier function evaluation before tape stripping and after every 5 tapes.
- s. Vital signs (Heart rate, respiratory rate, temperature, blood pressure) to be collected every 30 mins between 0 to 4 hrs. This applies to the first 2 infusions only.
- t. For the first 2 doses, the study drug will be infused over approximately 2 hours to reduce the risk for IRR, followed by at least approximately a 2 hour observation. For the subsequent infusions, the infusion time may be decreased to approximately one hour with a minimum of approximately 1 hour observation period.
- u. Triplicate ECG to be done pre dose and post end of first infusion (after approximately 2 hours), at Week 0 only.
- v. Vital signs (heart rate, respiratory rate, temperature, blood pressure) to be collected approximately every 30 mins between 0 to 2 hours for infusions 3 through 15. This does not apply to the first 2 infusions.
- w. Additional serial TEWL, SCH, and EIS measurements will be acquired after every 5 tape strips at Weeks 0, 4, and 16.

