4.4. End of Study Definition

End of Study Definition

The EOS is considered as the last scheduled study assessment shown in the SoA for the last participant in the study. The final data from the study site will be sent to the sponsor (or designee) after completion of the final participant assessment at that study site, in the time frame specified in the Clinical Trial Agreement.

Study Completion Definition

A participant will be considered to have completed the study if he or she has completed all scheduled study interventions through Week 15 and has completed all assessments at both Week 16 and Week 20 of the safety follow-up period.

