6. STUDY INTERVENTION AND CONCOMITANT THERAPY

6.1. Study Intervention Administered

Study intervention administration must be captured in the source documents and the electronic case report form (eCRF).

Bermekimab will be manufactured and provided under the responsibility of the sponsor. Refer to the [IB](#) for a list of excipients.

For details on rescue medications, refer to Section [6.8.4](#), Rescue Medication. For a definition of study intervention overdose, refer to Section [6.7](#), Treatment of Overdose.

Approximately 10 participants are planned to receive weekly 800 mg of IV bermekimab or placebo in Part A. Approximately 30 participants are planned to receive weekly 1200 mg of IV bermekimab or placebo in Part B. After the initial 10 participants (8A:2P) have completed 6 weeks of dosing in Part B, safety, PK, PD, and efficacy will be analyzed to determine an appropriate dose to be used in Part C. Approximately 20 participants are planned to receive the determined dose of bermekimab and placebo. The maximum dose to be considered for Part C will be 2400 mg IV weekly ([Table 2](#)).

Table 2: Description of Interventions

Part Name	Part A	Part B	Part C	N/A
Intervention Name	bermekimab	bermekimab	bermekimab	Placebo
Dose Formulation	sterile liquid formulation of 350 mg (175 mg/mL) of bermekimab in a prefilled syringe (PFS) with an injectable volume of 2.0 mL.	sterile liquid formulation of 350 mg (175 mg/mL) of bermekimab in a PFS with an injectable volume of 2.0 mL.	sterile liquid formulation of 350 mg (175 mg/mL) of bermekimab in PFS with an injectable volume of 2.0 mL.	Saline vials
Unit Dose Strength(s)	175 mg/mL	175 mg/mL	175 mg/mL	N/A
Dosage Level(s)	800 mg intravenous (IV) infusion weekly from Week 0 through Week 15	1200 mg IV infusion weekly from Week 0 through Week 15	TBD mg IV infusion weekly from Week 0 through Week 15	IV infusion weekly from Week 0 through Week 15
Route of Administration	IV infusion	IV Infusion	IV Infusion	IV Infusion
Use	Experimental	Experimental	Experimental	Placebo comparator
Investigational Medicinal Product	Yes	Yes	Yes	No
Non-Investigational Medicinal Product /Auxiliary Medicinal Product	No	No	No	No
Sourcing	Provided centrally by the sponsor			

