8.2.2. Vital Signs

Temperature, pulse/heart rate, respiratory rate, blood pressure will be obtained prior to study intervention administration at visits specified in the schedule of activities.

In addition, all participants will have an extended in-clinic observation period of approximately 4 hours during the first 2 infusions. In this period, vital signs will be taken at the following time points: 0 hour (start of infusion), 30 minutes, 1 hour, 1 hour and 30 mins, 2 hours (end of infusion), 2 hours and 30 mins, 3 hours, 3 hours and 30 mins, and 4 hours (post-infusion). Beyond the first 2 infusions, all participants will have approximately a 1 hour infusion period and at least a 1 hour observation post infusion, as well as vital signs taken every 30 minutes.

Blood pressure and pulse/heart rate measurements should be preceded by approximately 5 minutes of rest in a quiet setting without distractions (eg, television, cell phones).

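### Schedule of Activities footnote v ends serial vital signs at infusion 15, but Weeks 0 to 15 hold 16 infusions, so the Week 15 infusion is in neither vital-signs footnote

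*Protocol*

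**What the plan says.** **Dosing.** Table 2 (Protocol Section 6.1) gives the Part A regimen as "800 mg intravenous (IV) infusion weekly from Week 0 through Week 15", and Parts B, C and placebo have the same weeks. Section 4.4 agrees: a participant completes the study only after having "completed all scheduled study interventions through Week 15" and attending the later assessments.

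**Serial vital signs in the Schedule of Activities (Section 1.3).** Two footnotes divide the infusions between them.

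- Footnote s sets half-hourly readings from 0 to 4 hours and adds: "This applies to the first 2 infusions only".
- Footnote v sets readings "approximately every 30 mins between 0 to 2 hours for infusions 3 through 15", and says that it does not apply to the first two infusions.

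The row label that carries footnote v reads "except Weeks 0 and 1", with no other exception. Footnote t, on infusion time, keeps later infusions "with a minimum of approximately 1 hour observation period".

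**Serial vital signs in the body text.** Section 8.2.2 says: "Beyond the first 2 infusions, all participants will have approximately a 1 hour infusion period and at least a 1 hour observation post infusion", with vital signs every 30 minutes. The synopsis and Section 4.1 carry the same requirement, "as well as vital signs taken approximately every 30 minutes". None of the three names a last infusion. SAP Section 1.2 repeats the open-ended form.

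**The concern.** Footnote v counts in infusions, while the dosing schedule counts in weeks starting from zero. The two counts differ by one. If the last dose is at Week 15, the last infusion is number 16, and a footnote that stops at 15 leaves it out.

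The footnote matters because it instructs sites. Section 8.2 says that safety evaluations follow the time points in the Schedule of Activities, and site staff commonly work from that table. A site that reads footnote v literally could skip the half-hourly readings at the final infusion, although Section 8.2.2 requires them. A monitor would then have two conflicting texts against which to judge whether the missing readings are a deviation.

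The readings serve a purpose at every infusion. Table 1 in Section 2.3.1 warns that serious hypersensitivity reactions can occur at any time. Section 4.2.1 states that the intravenous dose levels and frequency are higher than previously studied. Section 7.1 makes symptomatic hypotension, defined by systolic thresholds, part of a criterion for stopping study drug.

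**Working it through.** This is a direct count; no statistical formula applies.

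**Inputs**

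- First dose Week 0, last dose Week 15, weekly (Table 2, Section 6.1; last dose confirmed in Section 4.4).
- Footnote s: infusions 1 and 2 (Section 1.3).
- Footnote v: infusions 3 to 15 (Section 1.3).

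**Step 1. Number of infusions.** Last week − first week + 1 = 15 − 0 + 1 = 16. Infusion n falls at Week n − 1, so infusion 15 is at Week 14 and infusion 16 is at Week 15.

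**Step 2. Coverage by the footnotes as written**

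| Source | Infusions | Weeks | Count |
|---|---|---|---|
| Footnote s | 1–2 | 0–1 | 2 |
| Footnote v | 3–15 | 2–14 | 15 − 3 + 1 = 13 |
| Both together | 1–15 | 0–14 | 2 + 13 = 15 |
| Scheduled | 1–16 | 0–15 | 16 |

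Omitted: 16 − 15 = 1, namely infusion 16 at Week 15.

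**Step 3. Could the numbers in footnote v be weeks?** Reading 3 through 15 as week numbers brings Week 15 in but drops Week 2, because footnote s ends at Week 1. One infusion is still uncovered. The footnote's own wording also counts in infusions, so this reading does not rescue it.

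**Step 4. Comparison with the body text.** The synopsis and Sections 4.1 and 8.2.2 cover every infusion after the first two: 16 − 2 = 14. Footnote v names 13 of them. The row label excepts only Weeks 0 and 1, which agrees with 14 and not with 13.

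**Step 5. Readings at risk.** Every 30 minutes from 0 to 2 hours gives 0, 30, 60, 90 and 120 minutes, which is 5 readings per participant at Week 15.

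**Step 6. After correction.** Infusions 3 to 16 number 16 − 3 + 1 = 14, and 2 + 14 = 16. None is omitted.

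The table grid did not survive extraction well, so the marks in its week columns were not used as evidence.

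**The case against.** The case for leaving this out is that it is a typing slip which the protocol already resolves. Three protocol sections and the SAP require the readings at every infusion after the first two. Section 8.2.2, which is the specific vital-signs section, presents its serial schedule as additional to the pre-dose readings at scheduled visits. A site that reads it therefore has an explicit instruction for Week 15, and nothing in the documents shows that any site would prefer the footnote.

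The count of five may also be too high. Section 8.2.2 requires a pre-dose reading at scheduled visits. If Week 15 is marked in the table, that reading would nearly duplicate the 0-minute one, leaving about four at risk.

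The clinical consequence is small as well. Reported infusion reactions came with the first or second infusions (Table 1). Footnote t keeps about an hour of observation after later infusions. Section 8.2.8 keeps the longer infusion and observation for anyone who has had a Grade 2 reaction. The SAP records early termination with few participants and only lists markedly abnormal vital signs.

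All of this stands as to weight, and five is best read as an upper bound. None of it changes the count. Footnote v remains wrong by one and in conflict with the body text. The summary of changes describes superseded text and proves nothing about the current wording. It does mention a vital-signs footnote being moved to Week 15 as the week of the last dose, which would fit a week number having been carried over as an infusion number.

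**Conclusion.** The point holds. Footnote v is wrong by one: footnotes s and v together cover 15 of the 16 scheduled infusions and leave out the one at Week 15.

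Its size is 1 of 16 infusions, or 1 of the 14 after the first two, with at most five serial readings per participant. Those readings are lost only if a site follows the footnote in preference to Section 8.2.2. Read as a whole, the protocol does not leave the last infusion unmonitored. No endpoint, sample size, estimand or error rate depends on the correction, so this is a minor point of accuracy and site instruction.

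The conclusion rests on two things stated in the documents: that dosing is weekly from Week 0 through Week 15 with both ends included, and that footnote v counts infusions.

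**What to change.** Change footnote v so that it applies to infusions 3 through 16 (Weeks 2 through 15). Giving the weeks beside the infusion numbers removes the ambiguity between the two counts and brings the footnote into line with Table 2, the synopsis and Sections 4.1 and 8.2.2.

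The cost is one number and a short parenthesis in a footnote. No procedure, visit or participant burden is added, because the body text already requires the readings. With the study terminated early, the remaining use is in judging any deviations recorded at Week 15 visits and in keeping the slip out of later protocols that reuse this table.
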